3.3.2 Intention-To-Treat Population

The ITT population are all randomised participants and they will be analysed according to the treatment group to which they were randomised at baseline. Missing outcome data will be imputed. Participants who had bariatric surgery during the study period will be included in this population.

Missing primary outcome data will need to be imputed for the ITT analyses; this will be done by assuming that these participants did not achieve $\geq 15\%$ weight loss at 52 weeks, which is a conservative approach.

3.3.3 Per Protocol Population

The per protocol population is defined as all participants who were compliant with their randomised treatment group, analysed according to the treatment group to which they have randomised at baseline. Participants in the standard care group are defined as treatment compliant if they complete at least 70% of the planned contacts in the Tier 3 service. Participants in the intervention group are defined as treatment compliant if they complete at least 70% of the planned contacts in the Tier 3 service, and take at least 70% of their planned doses of LIRA 3mg as stipulated by the prescribing pathway.

Participants that had Liraglutide 3mg outside of the treatment pathway (i.e. in the control group or in the intervention group after a stopping rule means they should have stopped taking Liraglutide 3mg) will be excluded from the per protocol population. The protocol deviations and in particular deviations from randomised treatment group in the protocol deviations will capture where this has occurred for any individual.

Participants who had bariatric surgery during the study period will be only be included at time-points prior to their bariatric surgery. They will be excluded from time-points after their bariatric surgery.

The binary variable of compliant with tier 3 service at 52 weeks will be used to exclude individuals that did not have 70% of planned visits for outcomes assessed at 52 weeks, likewise for outcomes assessed at 104 weeks the variable at 104 weeks will be used.

Individuals in the intervention arm that did not receive 70% of the doses as determined by the protocol (i.e. in the first 16 weeks or there after whilst continuing to meet the continue rules of the protocolised treatment schedule) will be excluded from the per protocol populations. The number of days taking LIRA and whether this corresponds to 70% of doses is defined in Appendix 7 in section 14. For outcomes at

the 52 week time point the definition in 14.1 should be used; while for outcomes at the 104 week time point the definition in 14.2 should be used.

3.3.4 Responder Population

The Responder population is defined as all participants in the intervention group who achieved $\geq 15\%$ weight loss at 52 weeks, and all participants in the standard care group. Participants will be analysed according to the treatment group to which they were randomised at baseline.

Participants who had bariatric surgery during the study period will be only be included at time-points prior to their bariatric surgery. They will be excluded from time-points after their bariatric surgery.

3.3.5 Safety Population

All individuals randomised into the trial will be in the safety population. Individuals randomised to the intervention will be analysed in the intervention arm unless they have not received a dose of LIRA on the prescribed treatment pathway i.e. the protocol deviations and in particular a deviation from randomised treatment group indicates this is the case. Individuals randomised to the control arm will be analysed in the control arm unless they have received a dose of LIRA as part of the prescribed treatment pathway i.e. the protocol deviations and in particular a deviation from randomised treatment group indicates this is the case.

4 General Issues for Statistical Analysis

4.1 Analysis Groups

In all analyses, participants will be analysed in the group to which they were randomised at baseline; importantly, the participants in the intervention group who stop LIRA 3mg, because they meet a pre-specified stopping rule, will still be analysed in the intervention group.

4.2 Missing Data

Attempts will be made to assess the primary outcome on all participants including those who have withdrawn from treatment. The number of missing observations for each outcome will be reported. If missing outcome data are present then the initial analysis will be based on the complete cases. A sensitivity analysis will then be carried out repeating the analyses with the ITT population to assess the possible impact of the missing data on the results produced. Missing primary outcome data will need to be imputed for the ITT analyses; this will be done by assuming that these participants did not achieve $\geq 15\%$ weight loss at 52 weeks, which is a conservative approach. We will also attempt to address bias by comparing the characteristics of those with missing outcome data to those who have completed follow-up. This strategy for dealing with missing outcome data has been recommended by White et al. (White 2011)

There should be no missing covariate data because site and baseline BMI are used as part of the randomisation process. The other covariate is treatment group which was assigned as part of the randomisation process and will be known for all participants.

Where participants were lost to follow up or missed a study visit, the study team attempted to access primary outcome data from existing hospital, GP or health records, where appropriate consent was in place.

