After 32 weeks (\pm 14 days) on the medication, only those participants who have lost $\geq 10\%$ of their baseline weight and are still on treatment with LIRA 3mg will be offered another 20 weeks on LIRA 3mg. Participants who have not met this weight loss target will have their LIRA 3mg treatment stopped but will still continue in the targeted prescribing pathway but will receive standard care only during the remainder of the study.

3rd stopping rule: After the first year of treatment (week 52; \pm 14 days), only those participants who have lost $\geq 15\%$ of their baseline weight and are still on treatment with LIRA 3mg will be offered another 52 weeks on LIRA 3mg. Participants who have not met this weight loss target will have their

LIRA 3mg treatment stopped and will still continue in the targeted prescribing pathway but will receive standard care only during the remainder of the study.

Participants who fail to reach the pre-defined weight-loss targets to continue LIRA 3mg treatment, or who choose to stop receiving LIRA 3mg, will continue to be offered the standard care provided by the Tier 3 service. These participants will still attend the Clinical Review Visits but not the additional visits for participants who are still on LIRA 3mg (e.g. Weeks 65 & 91) because these visits will not be relevant to them; visits at Weeks 65 and 91 are intended to provide a new prescription of LIRA 3mg and to discuss adherence and any side effects; see Appendices 2 & 3).

Participants will remain routinely in the Tier 3 service in-line with NICE guidance throughout the duration of the research study. Participants may be offered treatment options within the duration of the study, including bariatric surgery, as per NICE guidance and according to the decision of the local Tier 3 Multidisciplinary Team. Participants who have undergone bariatric surgery after randomisation will only be included in the intention to treat (ITT) analysis. This decision was made because the proportion of participants undergoing bariatric surgery is likely to be unbalanced between the treatment groups (i.e. more participants in the control group are expected to have bariatric surgery than in the targeted prescribing pathway treatment group), and thus weight loss in these individuals could unduly influence the study results. Participants who have been prescribed and start anti-obesity medication (such as Orlistat) will be ineligible for LIRA 3mg treatment.

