3.3.1 Complete Cases Population

The complete cases population is defined as all randomised participants who have data available for the outcome being analysed, according to the study group to which they were randomised at baseline. Participants who had bariatric surgery during the study period will be only be included at time-points prior to their bariatric surgery. They will be excluded from time-points after their bariatric surgery.

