5.3 Demographic and Baseline Characteristics

Baseline characteristics of the participants will be summarised by randomisation group and overall using mean (standard deviation) and median (interquartile range) for continuous variables and count (percentage) for categorical variables. There will be no tests of statistical significance nor confidence intervals for differences between randomised groups on any baseline variable.

Additionally, the baseline characteristics of those with missing primary outcome data will be summarised separately from those with complete primary outcome data using mean (standard deviation) and median (interquartile range) for continuous variables and count (percentage) for categorical variables. These characteristics will be compared using a t-test for normally distributed variables, a Mann-Whitney test for non-normally distributed variables, and a chi-squared test for categorical variables.

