5.4.1 Primary Analysis of Primary Outcome

The primary analysis will compare the proportion of participants achieving $\geq 15\%$ weight loss at 52 weeks (primary outcome) after randomisation between the two randomisation groups. The primary outcome will be summarised using count and percentage. A logistic regression model will be used with a binary indicator showing whether or not $\geq 15\%$ weight loss was achieved at 52 weeks as the outcome, randomisation group (intervention or control) as the main covariate, and the stratification factors of site (non-ordinal categorical variable) and baseline BMI ($\geq 45\text{kg}/\text{m}^2$; $<45\text{kg}/\text{m}^2$) as additional covariates. The adjusted odds ratio will be presented, 95% confidence interval and p-value comparing the two groups.

The primary analysis will use the complete cases population, therefore missing data will not be imputed.

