5.4.2 Secondary Analyses of Primary Outcome

The primary analysis of the primary outcome will be repeated using the ITT and per protocol populations as secondary analyses. Missing primary outcome data will need to be imputed for the ITT analyses; this will be done by assuming that these participants did not achieve $\geq 15\%$ weight loss at 52 weeks, which is a conservative approach.

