5.4.3 Sensitivity Analyses

No sensitivity analyses are planned.

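### The ITT rerun meant to test missing data also changes the bariatric-surgery rule, nothing else tests it, and counting missing as failure is not always conservative for the odds ratio

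*SAP*

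**What the plan says.** - **Primary analysis.** SAP 5.4.1: "The primary analysis will use the complete cases population, therefore missing data will not be imputed". The model is a logistic regression adjusted for site and BMI stratum, reported as an odds ratio.
- **Surgery in complete cases.** SAP 3.3.1 on operated participants: "They will be excluded from time-points after their bariatric surgery".
- **Missing-data check.** SAP 4.2 describes a sensitivity analysis "repeating the analyses with the ITT population to assess the possible impact of the missing data on the results produced".
- **ITT rules.** SAP 3.3.2 counts a missing primary outcome as not reaching 15%, and on surgery says: "Participants who had bariatric surgery during the study period will be included in this population". SAP 5.4.2 justifies the imputation with the words "weight loss at 52 weeks, which is a conservative approach".
- **Anything further.** SAP 5.4.3: "No sensitivity analyses are planned". SAP 5.4.2 classes the ITT analysis as secondary, whereas 4.2 calls it a sensitivity analysis. The per-protocol analysis and its exploratory variant in 5.4.4 do not vary the missing-data assumption.
- **Who is missing.** SAP 5.3: "the baseline characteristics of those with missing primary outcome data will be summarised separately from those with complete primary outcome data". Tables 16.5 and 16.6 make this comparison with the two arms pooled.
- **Expected surgery.** Protocol 6.2: "more participants in the control group are expected to have bariatric surgery than in the targeted prescribing pathway treatment group".

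**The concern.** A missing-data sensitivity analysis is informative when it changes the missing-data assumption and holds the rest fixed. Here the surgery rule changes too. The protocol expects surgery to be unbalanced between arms (6.2) and expects operated participants to lose substantial weight (11.1). If the complete-case and ITT odds ratios differ, the reader cannot tell which rule moved them. If they agree, two shifts may have cancelled.

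Counting missing as failure lowers the success proportion in each arm. What it does to the odds ratio depends on how much is lost in each arm, and in an open-label trial offering the drug to one arm only, unequal loss is plausible. The pooled baseline comparison cannot show whether the people lost differ between arms.

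The result at stake is the main robustness statement for the primary endpoint. It could reassure wrongly, or suggest a missing-data problem that is really a surgery effect.

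**Working it through.** **Inputs from the documents.** 261 intervention and 131 control; success 16% v 5%; 25% dropout; two-sided 5% (Protocol 11.2; SAP 1.2.4, 4.6). Success at 56 weeks was 24.2% in early responders and 1.8% in early non-responders (Protocol 4).

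**Assumed.** Loss by arm, surgery counts before week 52, success after surgery, and loss by early response. Odds ratios below are expected and unadjusted.

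**The plan's own figure.** A two-proportion calculation without continuity correction needs 96 + 192 = 288, and 288/0.75 = 384 against the stated 392. Power at 75% of 131 and 261 is 81.2%, so the stated size reproduces closely.

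**Step 1: missing = failure alone.** Each proportion becomes p(1 − m), where m is the loss. The true OR is (0.16/0.84)/(0.05/0.95) = 3.62. Every row has 25% overall loss.

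| Loss, intervention / control | Proportions | OR |
|---|---|---|
| 25% / 25% | 12.0% v 3.75% | 3.50 |
| 30% / 15% | 11.2% v 4.25% | 2.84 |
| 20% / 35% | 12.8% v 3.25% | 4.37 |
| 15% / 45% | 13.6% v 2.75% | 5.57 |

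**Step 2: both rules at once.** Non-operated successes before loss are 0.16 × 261 = 41.76 and 0.05 × 131 = 6.55, with loss at random within arm. In each arm k participants are operated before week 52, all with a weight recorded, and s of them reach 15%. With S the non-operated successes and n the arm size:

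- complete case: S(1 − m) / [(n − k)(1 − m)]
- planned ITT: [S(1 − m) + s] / n
- missing = failure under the complete-case surgery rule: S(1 − m) / (n − k)

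| Loss, int / ctl | k, int / ctl | s, int / ctl | Complete case | Planned ITT | Surgery rule fixed |
|---|---|---|---|---|---|
| 20% / 35% | 1 / 1 | 1 / 1 | 3.61 | 3.63 | 4.35 |
| 25% / 25% | 1 / 1 | 1 / 1 | 3.61 | 2.99 | 3.49 |
| 25% / 25% | 3 / 7 | 2 / 5 | 3.46 | 1.79 | 3.35 |

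In row 1, planned-ITT successes are 33.41 + 1 of 261 and 4.26 + 1 of 131. The ITT appears to confirm the primary result only because the surgery effect offsets the missing-data effect. In row 2 the OR falls by 0.62, of which 0.12 is missing data. In row 3 it falls by 1.67, of which 0.11 is missing data.

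**Step 3: loss related to outcome.** The early-responder share that gives 16% overall is r = (0.16 − 0.018)/(0.242 − 0.018) = 0.634. Suppose 10% of early responders and 51% of early non-responders are lost in the intervention arm (25% overall), and 25% of control at random.

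- Retained intervention successes: 0.634 × 0.90 × 0.242 + 0.366 × 0.49 × 0.018 = 0.1413.
- Complete case: 0.1413/0.75 = 0.188 v 0.05, OR 4.41.
- Missing = failure: 0.1413 v 0.0375, OR 4.22.

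Both exceed 3.62, so they would seem to support each other. If the same retention (88.3% of successes, 72.5% of failures) applied in both arms, complete case would be unbiased at 3.62 and missing = failure would give 3.56.

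**The case against.** - **Effect scale.** The trial was sized on an absolute difference of 11 points. On that scale every Step 1 row shrinks the effect: 8.25, 6.95, 9.55 and 10.85 points. Inflation needs 0.05 × control loss to exceed 0.16 × intervention loss, a ratio above 3.2. This is correct and limits the criticism, but the SAP reports an odds ratio, and even on the difference scale the direction depends on loss by arm.
- **Assumed inputs.** The documents give no loss by arm, no surgery count before week 52 and no success rate after surgery. Only surgery before week 52 matters here. The 52-week retention measures (wider visit window, home weights, record linkage, incentive payment) should also reduce loss. So the examples show what can happen, not how large it will be.
- **Sparse data.** Control contributes about four to five expected successes. The three odds ratios in row 1 of Step 2 have 95% intervals of about 1.27–10.23, 1.41–9.33 and 1.55–12.22. A shift of this size is well within sampling error. The analyses share participants, however, so overlapping intervals do not rule out a systematic shift.
- **Partly recoverable.** Table 16.1 counts operated participants by arm, and Table 16.7 gives numbers with data and with the outcome. ITT successes minus complete-case successes equals operated successes. Crude counts can therefore be separated by hand, but there is no surgery timing and no adjusted estimate, interval or p-value.
- **Imputation.** Multiple imputation adds model assumptions in a small control arm, and LIRA status does not vary there. That is a reason to make it a sensitivity analysis, not a reason to omit it.

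No type I error claim is made. At a common 5% rate the unadjusted logistic Wald test rejects only 2–3% of the time in the equal-loss, 20%/35% and 15%/45% cases.

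**Conclusion.** The concern holds and should be fixed. The plan provides no adjusted analysis in which only the missing-data rule changes, so the complete-case v ITT comparison cannot do what SAP 4.2 asks of it. That follows from the text alone.

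The size is illustrative. At the planned rates and 25% overall loss, missing = failure puts the OR anywhere from 2.84 to 5.57 around a true 3.62, depending on how loss splits between arms. A single operated success per arm is enough to hide that movement or to imitate it. These figures rest on assumed loss and surgery and ignore the site and BMI adjustment. The unconditional description of the rule as conservative is not justified for the reported measure. The choice of complete case as the primary analysis is not in dispute here.

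**What to change.** Keep complete case as primary and amend SAP 4.2, 5.4.2 and 5.4.3:

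1. Run missing = failure, and any other missing-data sensitivity analysis, under the same surgery rule as the complete-case analysis. Report the ITT analysis that includes post-surgery weights separately, and give it the same label in 4.2 and in section 5.
2. Add a sensitivity analysis that multiply imputes week-52 weight by arm and then applies the 15% cut. Use site, baseline weight or BMI, weights at weeks 8, 16 and 32 (plus optional visits where available), and LIRA status in the intervention arm. Follow it with a tipping-point analysis that varies the assumption separately by arm.
3. Report missing outcomes and surgery before week 52 by arm, and split Tables 16.5 and 16.6 by arm.
4. Replace the statement that the rule is conservative with one saying that its direction depends on the loss in each arm.

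The cost is SAP wording and modest programming, with no new data. Interim weights from optional visits will be incomplete, and the imputation and tipping-point analyses bring their own assumptions. The SAP is marked as a draft and allows amendment before database lock. If lock has passed, the analyses can still be run and labelled post hoc.

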4.3 Derived/ Computed Variables

Analyses will be adjusted for the stratification variables which are study site and body mass index (BMI).

Study site is a non-ordinal, categorical, dummy variable with a unique code for each site.

BMI is a continuous variable calculated as weight in kg divided by height in metres squared. For stratification purposes, baseline BMI was dichotomised based on cut-off values of $\geq 45\text{kg}/\text{m}^2$ and $< 45\text{kg}/\text{m}^2$. This dichotomised grouping will be included in statistical models.

4.4 Multiple Testing

No corrections will be made for multiple testing. However, due to the large amount of secondary outcomes, statistical models will only be fitted for the most important secondary outcomes to limit the impact of multiple testing. Descriptive summaries will be produced for the other secondary outcomes without multiple testing, as described below.

4.5 Analysis Software

Latest version of Stata, SAS, or other appropriate statistical software.

4.6 Statistical Significance

All statistical tests, p-values, and confidence intervals will be two-sided. Statistical significance will be assessed at the 5% level for main effects. No interaction analyses are planned, however if post-hoc interaction effects are tested then these will be assessed at the 10% level.

4.7 Outliers

Given that the study participants are taking part in this study because of issues around weight control, outliers will not be removed from the dataset as these could feasibly be genuine extremes.

5 Statistical Methodology

5.1 Disposition

A CONSORT diagram showing the flow of participants through the study will be produced, including the number of screened and treated participants. This diagram will also show the number of participants receiving the allocated treatment at each stage of the study, along with the reasons for stopping treatment. In particular, the number who stop LIRA 3mg due to each stopping rule will be clearly stated.

The number (percentage) of participants in each analysis population will be tabulated overall and by treatment group. The type and number (percentage) of protocol deviations will also be tabulated overall and by treatment group in the ITT population.

5.2 Interim analysis

No interim analysis is planned.

5.3 Demographic and Baseline Characteristics

Baseline characteristics of the participants will be summarised by randomisation group and overall using mean (standard deviation) and median (interquartile range) for continuous variables and count (percentage) for categorical variables. There will be no tests of statistical significance nor confidence intervals for differences between randomised groups on any baseline variable.

Additionally, the baseline characteristics of those with missing primary outcome data will be summarised separately from those with complete primary outcome data using mean (standard deviation) and median (interquartile range) for continuous variables and count (percentage) for categorical variables. These characteristics will be compared using a t-test for normally distributed variables, a Mann-Whitney test for non-normally distributed variables, and a chi-squared test for categorical variables.

5.4 Primary Outcome Analysis

The complete cases, ITT, and per protocol analyses will compare the two groups to demonstrate the effectiveness of the targeted prescribing pathway compared with standard care.

5.4.1 Primary Analysis of Primary Outcome

The primary analysis will compare the proportion of participants achieving $\geq 15\%$ weight loss at 52 weeks (primary outcome) after randomisation between the two randomisation groups. The primary outcome will be summarised using count and percentage. A logistic regression model will be used with a binary indicator showing whether or not $\geq 15\%$ weight loss was achieved at 52 weeks as the outcome, randomisation group (intervention or control) as the main covariate, and the stratification factors of site (non-ordinal categorical variable) and baseline BMI ($\geq 45\text{kg}/\text{m}^2$; $<45\text{kg}/\text{m}^2$) as additional covariates. The adjusted odds ratio will be presented, 95% confidence interval and p-value comparing the two groups.

The primary analysis will use the complete cases population, therefore missing data will not be imputed.

